1.1 Overview of Disease and Treatment

1.1.1 Overview of Tenosynovial giant cell tumors (TGCT)

Tenosynovial giant cell tumors (TGCT) is a rare, locally invasive soft tissue tumor arising from the synovium of joints, bursa, and myosheaths, manifested by pain, swelling, stiffness, hemorrhagic joint effusion, periarticular erosion, cartilage degeneration, and secondary osteoarthritis in the affected joints. TGCT is generally not life-threatening, but some patients are not amenable to surgical excision and have a high risk of recurrence. Repeated surgeries are prone to lead to severe joint injury and surgical complications, and have a high risk of amputation, which has a serious impact on the quality of life of patients.¹ The World Health Organization (WHO) unified TGCT into diffuse and localized type² in 2013. Localized TGCT accounting for approximately 80-90% of all cases, mostly located in fingers and feet, is mainly treated with surgery, but still has a recurrence rate of up to 15%. Diffuse TGCT is a devastating and locally invasive tumor, usually involving larger joints, such as the knee, hip, and ankle. Although this subtype accounts for only 10-20% of all cases, surgical treatment is difficult and the tumor cannot be completely resected, resulting in a 5-year recurrence rate of approximately 45%.³

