recurrence in patients with localized TGCT is lower than in patients with diffuse TGCT, the 10-year recurrence rate still exceeds 10%.¹⁸ These studies suggest that a high recurrence rate will limit the long-term benefit of surgical treatment in patients with TGCT. Repeated surgery can lead to serious joint damage and limb amputation risk.

Since aberrant expression of CSF-1 is an important genetic basis for the development of TGCT, preliminary progress has been made in targeted systemic therapies targeting the CSF-1/CSF-1R pathway. Imatinib and Nilotinib are two tyrosine kinase inhibitors that block multiple proteins, including CSF-1R, and may have limited antitumor activity in TGCT.^{19,20,21} The guidance issued by the National Comprehensive Cancer Network (NCCN) for soft tissue tumors (2022.v2) recommended Imatinib and Nilotinib as class 2 systemic therapy agents for the treatment of TGCT.²² Pexidartinib was approved by the US FDA in 2019 and it is recommended as the only one of class 1 systemic therapy agents for TGCT in the NCCN guideline. This is primarily based on the success of a Phase 3 randomized, double-blind, placebo-controlled study.²³ Pexidartinib treatment (n = 61) had a higher ORR at Week 25 compared with placebo (n = 59) (39% vs 0%; P < 0.0001).²³ However, the potential risk of fatal liver injury for this drug cannot be ignored, with a boxed warning of the risk of serious and potentially fatal liver injury in the package insert.²⁴

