5.7 Blinding and Unblinding

5.7.1 Blinding

Part 1 will be a randomized, placebo-controlled, double-blind study, where treatment assignment will remain unknown to the patients, Investigators, study site personnel, safety laboratory personnel, central imaging readers and reviewers, and the sponsor. The appearance of ABSK021 and placebo capsules will be identical.

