6.3.6 Progressive Disease Follow-up

Patients who discontinue treatment prematurely for reasons other than disease progression will be followed for disease progression until disease progression, death, loss to follow-up, or the patient receives alternative anti-tumor therapy (including surgery), whichever occurs first. Disease progression follow-up will be conducted every 12 weeks (± 7 days). In principle, the maximum follow-up time will not exceed 12 months.

For patients who withdraw from the study after prematurely treatment discontinuation and plan to undergo surgery, it is recommended to perform the surgery at least 3 weeks after the last dose (for patients in Part 1, the Investigator and the sponsor will jointly decide whether emergency unblinding is needed). Details of the surgery will be collected, including but not limited to, the reason for surgery, date, surgery name, copies of the surgical report and pathological reports (if any), ROM and PRO assessments (if any). Surgically resected tumor samples will be collected to assess the effect of this study drug on tumor cells, and disease recurrence will also be followed up by telephone (every 3 months) for a maximum follow-up period up to 12 months after the surgery (not applicable for placebo-treated patients).

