5.5.4. New Anti-Cancer Therapy

The number and percentage of patients receiving any new anti-cancer surgery, surgery location, surgery intent, pathological results after surgery and recurrence will be summarized by treatment group and overall.

Patients receiving any other new anti-cancer therapies other than surgery will be listed.

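### SAP 5.5.4 tabulates recurrence after surgery by treatment group, but Protocol 6.3.6 requires no recurrence follow-up in patients who received only placebo

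*Protocol*

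**What the plan says.** Protocol 6.3.6 has two parts.

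- Patients who stop treatment early without progression are followed for progression every 12 weeks. That follow-up stops at progression, death, loss to follow-up, "or the patient receives alternative anti-tumor therapy (including surgery), whichever occurs first".
- Patients who withdraw after stopping early and plan surgery have the operation documented. In addition, "disease recurrence will also be followed up by telephone (every 3 months"). The sentence then sets the length of these calls and exempts one group: "for a maximum follow-up period up to 12 months after the surgery (not applicable for placebo-treated patients"). For Part 1 patients, "the Investigator and the sponsor will jointly decide whether emergency unblinding is needed".

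Protocol 5.7.1 states that in Part 1 "treatment assignment will remain unknown to the patients, Investigators, study site personnel", among others.

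SAP 5.5.4 describes a number-and-percentage table for new anti-cancer surgery. Its last items are "pathological results after surgery and recurrence will be summarized by treatment group and overall". The section does not limit the recurrence item to patients exposed to ABSK021, does not say who forms its denominator, and has no category for patients who were not followed. SAP section 9 lists no departures from the protocol.

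**The concern.** The SAP promises a figure that the protocol does not arrange to collect. If both documents are followed to the letter, recurrence is actively sought for up to a year in operated patients who received ABSK021 and need not be sought in those who received only placebo. With the same true recurrence in both, the table could show events under ABSK021 and none under placebo. A reader could take that as more recurrence after the drug, when it would reflect who was telephoned.

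The exemption also depends on knowing the arm. A site that stays blinded cannot tell whom to leave out and may call everyone. Whether a placebo-only patient is followed may therefore turn on whether that patient was unblinded before surgery.

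**Working it through.** The plan states no figure for this item, so there is nothing to reproduce. The check compares the texts and then looks at what the table would show.

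**1. Is there another route to a recurrence in an operated placebo-only patient?**

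- Progression follow-up (Protocol 6.3.6; Table 1, footnote 5): ends at surgery.
- Recurrence calls (Protocol 6.3.6): placebo-treated patients are exempt.
- Safety follow-up (Table 1, footnote 4): one contact about 30 days after the last dose, for adverse events and concomitant medications.
- Remaining Part 1 visits (Protocol Table 7): patients who stop treatment without progression are encouraged to stay until Part 1 ends. A Week 25 MRI might show a recurrence, but attendance is not required and no visit extends to 12 months after surgery.

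None of these requires recurrence to be ascertained.

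**2. Who is affected?** The surgery paragraph in 6.3.6 and the table in SAP 5.5.4 both cover the whole study; Part 1 appears in that paragraph only in connection with unblinding. A placebo patient who enters Part 2 receives open-label ABSK021 and is most naturally no longer placebo-treated. The gap therefore concerns patients randomised to placebo who never received ABSK021. Surgery details and pathology reports are requested without distinction by arm, so only the recurrence item is affected.

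**3. What would the row show?** Let r be the true recurrence proportion, the same in all operated patients; a the number of operated ABSK021-exposed patients, all followed; and p the number of operated placebo-only patients, none followed and none reporting spontaneously.

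- Denominator of all operated patients: ABSK021 shows r, placebo shows 0, and overall shows r × a / (a + p), which is below r whenever p > 0.
- Denominator of followed patients: ABSK021 shows r, placebo has no estimate, and overall shows r, which is simply the ABSK021 figure again.

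Purely as illustration, with assumed values (the documents give neither surgery counts nor a recurrence rate for this trial), take r = 10% and the first denominator:

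- a = 6, p = 3: overall = 0.10 × 6 / 9 = 6.7%.
- a = 3, p = 6: overall = 0.10 × 3 / 9 = 3.3%.

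So the overall figure is understated under one choice of denominator and not under the other. The placebo figure is uninformative under both.

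**4. Follow-up effort.** 12 months / 3 months = up to 4 calls per ABSK021-treated surgery patient, against 0 required per placebo-only patient.

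**The case against.** The strongest reply is that the exemption is deliberate. The same sentence of 6.3.6 collects resected tissue to study the drug's effect on tumour cells, and a patient never exposed has nothing to add to that question. Recurrence after surgery is not an objective or endpoint, and SAP 5.5.4 sits among the background characteristics with no test attached. This is fair, and it is why the preferred remedy accepts the exemption and changes the SAP. It does not explain why the SAP then reports recurrence for the placebo group.

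A second reply is that SAP 4.2.1 analyses observed values without imputation, so unfollowed patients would not be counted as recurrence-free. Where the SAP wants missing data treated as an outcome it says so, as for a missing Week 25 MRI (6.3.2) and for BPI-30 (6.4.5). This has weight: a reader might infer that the overall figure is bound to be too low, and the documents do not establish that. But the general rule does not fix the denominator of a number-and-percentage table, where no recorded recurrence looks the same as recurrence not sought.

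Third, a blinded site that calls everyone removes the imbalance. That is true for such patients, but the protocol does not require the calls, and nothing indicates how often the arm would be known.

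Fourth, there may be no such patients. Entry requires unresectable disease, and placebo patients are offered ABSK021 after Part 1, or earlier on progression. This stands and limits the importance of the point.

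**Conclusion.** The mismatch holds and is minor. The placebo-only recurrence cell has no required ascertainment, and the overall percentage is understated if unfollowed patients remain in its denominator. This rests on the exemption being applied as written and on no spontaneous reports. The consequence is one potentially misleading descriptive row, outside the testing hierarchy; the primary endpoint, alpha, power and sample size are unaffected.

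Two stronger readings are tempting and should be resisted.

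- A reader might infer from the 2:1 allocation that about a third of all recurrences would go unseen, or half if the two groups had equal numbers of operations. The documents do not support either share: they give no surgery counts, and ABSK021 operations from all three parts, including those in switched patients, belong in the table.
- A reader might convert the background recurrence rates in Protocol 1.1.1 and 1.1.3 into a chance of missing an event here. Those rates come from surgically treated patients, whereas this trial enrols patients judged unresectable, and the number of placebo-only operations is unknown. No credible probability follows.

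**What to change.** **Preferred, in SAP 5.5.4.** Restrict the recurrence row to operated patients who received ABSK021, including placebo patients who switched. Use those with recurrence follow-up as the denominator, and footnote that recurrence was not followed after surgery in placebo-only patients. The other surgery items can stay by treatment group and overall. The cost is one SAP edit, with no extra data collection and no protocol change. The downside is that recurrence has no placebo reference.

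**Alternative, in Protocol 6.3.6.** Lift the placebo exemption for the telephone calls only, so that every operated patient is called and a blinded site can follow the rule without knowing the arm. The parenthesis should not simply be deleted: it can be read as also covering resected-tissue collection, and removing it could extend that collection to patients never exposed to the drug. Any tissue exemption should be restated separately. The cost is up to 4 calls per placebo-only surgery patient and a protocol amendment with the usual ethics and regulatory approvals.

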6.4 Safety assessment

Safety assessments will include demographic information and disease history, physical examination, ECOG score, vital signs, 12-lead ECG and echocardiography/MUGA, laboratory safety assessments, pregnancy tests, concomitant medications and therapies, adverse events (AEs) and related items in NCI-PRO-CTCAE. Safety assessments will be performed according to the time points indicated in Table 1, [Table 2](#) and Table 3. Any persistent abnormalities with clinical significance at the end of treatment will be followed up by the Investigator until the abnormality relieves, stabilizes, or has a clear outcome based on clinical judgment or the end of the study.

6.4.1 Demographic Information and Disease History

Demographic information includes the patient's sex, year of birth, age, ethnicity, and race (as permitted by the local laws and regulations).

Demographic information, prior and current medical history as well as detailed tumor history, including prior anti-tumor therapy, will be collected at screening.

6.4.2 Physical examination

Physical examination may be performed by a qualified physician, physician assistant, or registered nurse. The examination includes general condition, skin, neck (including thyroid), eyes, ears, nose, throat, lungs, heart, abdomen, back, lymph nodes, extremities, blood vessels, and nervous system. Additional rectal, external genital, breast, and pelvic examinations are required if indicated by medical history or clinical symptoms. Physical examination is recommended to

focus on primary tumor sites, areas of known abnormalities, or informed by clinical findings and/or patients.

Weight information will be collected at each physical examination and height will only be collected at screening. A general physical examination will be performed at subsequent visits. Investigators may perform more frequent examinations if clinically indicated.

6.4.3 ECOG score

ECOG score (Appendix 12.1) will be performed concurrently with the physical examination.

6.4.4 Vital signs

Vital signs include sitting blood pressure, pulse, respiratory rate, and pre-dose body temperature. When PK sampling is performed, vital signs are recommended to be measured after ECG and before PK sampling.

6.4.5 12-Lead Electrocardiogram (ECG)

The 12-lead ECG will be performed at screening, all on-study visits, and at the EOT visit. ECGs will be performed pre-dose (within 1-hour pre-dose) and post-dose (3 ± 0.5 hours post -dose) on Cycle 1 Day 1 (C1D1) and Cycle 1 Day 15 (C1D15) in Part 1, and ECGs at the remaining time points will be performed at any time on the day of the visit. Additional ECG tests may be performed as clinically indicated. Blood draws for vital signs, PK, and safety are recommended to be performed after the ECG, if applicable. Patients are advised to remain supine or semi-recumbent for at least 5 minutes prior to ECG testing. ECG results will include heart rate (HR), RR interval, PR interval, QRS interval, QT interval, and QTcF interval.

6.4.6 Echocardiography (or MUGA)

In Part 1, echocardiography or MUGA will be performed at screening, C4D1 (± 7 days), and C7D1 (± 7 days). In Part 2, echocardiography or MUGA will be performed on C1D1 ($- 2$ days), C4D1 (± 7 days) and C7D1 (± 7 days). In Part 3, echocardiography or MUGA will be performed on C4D1 (± 7 days), C7D1 (± 7 days) and subsequent visits. Results will include clinically important findings and left ventricular ejection fraction (LVEF). The same examination (echocardiography or MUGA) should be used throughout the study. If the time interval between the current examination and the previous examination does not exceed 7 days, repeated examination is not needed.

6.4.7 Laboratory Safety Assessments

Clinical laboratory tests include pregnancy test (6.4.8), hematology, blood chemistry, myocardial enzymes, coagulation, urinalysis, thyroid function test, and virology. Specific evaluation requirements are as follows:

- Hematology includes red blood cell count, hemoglobin concentration, hematocrit, white blood cell count, differential and absolute value of white blood cells (including neutrophils count, lymphocytes count, monocytes count, eosinophils count, and basophils count), and platelet count.
- Blood chemistry includes sodium, potassium, chloride, bicarbonate/ $\text{CO}_2/\text{CO}_2\text{CP}$, BUN/Urea, glucose, creatinine, AST, ALT, LDH, gamma-glutamyl transferase, alkaline phosphatase, total and direct bilirubin, total protein, albumin, calcium, magnesium, phosphorus, cholesterol, triglycerides, lipase, and amylase (if lipase and amylase cannot be tested simultaneously, one of which can be selected according to local site conditions). In the event of \geq Grade 2 transaminase elevations, more frequent liver function tests (e.g., twice weekly transaminase tests, etc.) are recommended until recovery.
- Myocardial Enzyme tests include creatine kinase (CK) and creatine kinase isoenzyme (CK-MB). Cardiac troponin-T or cardiac troponin-I will be measured at baseline and further evaluation is recommended during the study if ECG morphology shows the possibility of myocardial ischemia or infarction, or if CK increases \geq Grade 3.
- Coagulation will be performed according to time points specified in [Table 1](#), [Table 2](#) and [Table 3](#). Tests included prothrombin time (PT), international normalized ratio (INR), activated partial thromboplastin time (APTT), fibrinogen (Fbg), and thrombin time (TT).
- Urinalysis includes specific gravity, glucose, total protein, ketones, and red blood cells. If urine protein is $\geq 2+$ at any visit time point, further evaluation is recommended, such as 24-hour urine protein quantification, at the Investigator's discretion.
- Thyroid function tests include TSH, FT3, and FT4. This will be performed according to time points specified in [Table 1](#), [Table 2](#) and [Table 3](#).
- Virological testing includes testing for HIV, HBV, and HCV infection. HIV infection will be tested by HIV-Ab. HBV infection will be tested by the hepatitis B virus surface antigen (HBsAg). If the test result of hepatitis B expressed antigen is positive, HBV-DNA test is required. HCV infection will be detected by hepatitis C virus antibody (confirmed by Western Blot or ELISA). If the test result is positive, hepatitis C RNA testing should be supplemented. Virological testing will be performed at screening.

6.4.8 Pregnancy test

For women of childbearing potential, a pregnancy test will be performed at the times indicated in [Table 1](#), [Table 2](#) and [Table 3](#) and will also be performed at the end of treatment. Of these, pregnancy tests at screening should be completed within 7 days prior to randomization. Refer to [8.2.2](#) for pregnancy reporting during the study.

Female patients of non-childbearing potential must meet either of the following and can be exempt from pregnancy testing:

- Postmenopausal women: spontaneous menopause for at least 12 consecutive months with serum FSH levels ≥ 40 mIU/mL.
- Hysterectomy or bilateral oophorectomy/salpingo-oophorectomy performed.
- Bilateral tubal ligation for at least 6 months.

All other female patients, including those with bilateral tubal ligation within 6 months and without hysterectomy, will be considered of childbearing potential.

6.4.9 Contraception

Patients participating in this study need to agree to use effective methods of contraception from at least 14 days prior to randomization until 6 months after the last dose of ABSK021. According to the requirement of the European authorities, patients from Europe need to agree to use of a highly effective contraceptive measure from at least 14 days prior to randomization until 6 months after the last dose of ABSK021. Methods that can achieve a failure rate of less than 1% per year when used consistently and correctly are considered as highly effective birth control methods.

Contraception methods can be exempt in following situations:

- If the patient has become accustomed to daily absolute abstinence lifestyle. Periodic abstinence (abstinence adjusted according to ovulation period) and extracorporeal ejaculation are not exempt from contraceptive measures.
- If a male patient has undergone bilateral orchiectomy or if the patient has no vas deferens confirmed by semen examination or ultrasound, which means the patient is not of childbearing potential prior to the first dose of study drug.
- Female patients of non-childbearing potential who meet either of the following conditions:
 - Postmenopausal women: spontaneous menopause for at least 12 consecutive months with serum FSH levels ≥ 40 mIU/mL.
 - Hysterectomy or bilateral oophorectomy/salpingo-oophorectomy has been performed.
 - Bilateral tubal ligation for at least 6 months.

Note: all other female patients, including those with bilateral tubal ligation within 6 months and without hysterectomy, will be considered of childbearing potential.

Acceptable highly effective contraception methods ²⁷:

- Hormonal contraception that inhibits ovulation, combined use of estrogen and progesterone^{*}:
 - Oral
 - Intravaginal
 - Transdermal
- Progestogen-only hormonal contraception associated with inhibition of ovulation^{*}:
 - Oral
 - Injection
 - Implantation
- Continuous use of an intrauterine device (non-hormonal) or an intrauterine hormone-releasing system (IUS) for at least 6 months^{*}.
- Bilateral tubal ligation for at least 6 months.
- Vasectomised partner^{**}.
- Sexual abstinence^{***}.
- Vasectomy for 6 months or more, with negative postoperative semen analysis.

^{*}: Hormonal contraceptives can be used as highly effective methods of birth control unless they are already prohibited in Section 5.9.3, as the efficacy of hormonal contraceptives may be affected by potential drug-drug interactions with ABSK021. Intrauterine devices and intrauterine hormone releasing systems are acceptable methods of contraception in the absence of definitive drug interaction studies when hormone exposures from intrauterine devices do not alter contraception effectiveness.

^{**}: Vasectomised partner is a highly effective birth control method provided that partner is the sole sexual partner of the WOCBP trial participant and that the vasectomised partner has received medical assessment of the surgical success. If not, an additional highly effective method of contraception should be used.

^{***}: Sexual abstinence is considered a highly effective method only if defined as refraining from heterosexual intercourse during the entire period of risk associated with the study treatments. The reliability of sexual abstinence needs to be evaluated in relation to the duration of the clinical trial and the preferred and usual lifestyle of the subject.

Acceptable contraception methods:

- Male/female condoms with or without spermicide ingredients.
- Barrier contraception (e.g., diaphragm, cervix cap, or contraceptive sponge) and spermicide.

- Barrier contraception without spermicide is acceptable in participating countries that do not use spermicides.

Other precautions:

- The above acceptable methods of contraception are only provided as examples. Some of these measures may be prohibited in accordance with local requirements. If there are any questions, the sponsor may be contacted.
- Female condoms should not be used with male condoms (as a dual contraceptive method), due to risk of condom(s) tearing.
- Patients who are not sexually active at screening should agree to comply with the contraceptive requirements of this study when having sex with the opposite sex.
- Other contraceptive requirements are required in accordance with local regulations and/or requirements, as applicable.
- Male patients should not donate sperm from the start of the first dose of study drug through the entire study and for 6 months after the last dose of study drug.
- Female patients and female partners of male patients must not plan to become pregnant within 6 months after the last dose of study drug.
- Contraceptive requirements must be met if the female partner of a male patient becomes pregnant through documented in vitro fertilization (sperm donation) or cryopreserved sperm (collected prior to receiving study drug). In this case, male patients must use an acceptable method of birth control (to ensure that the fetus does not come into contact with the study drug) during the study until 6 months after receiving the last dose of study drug.

Special circumstances that do not meet the above description need to be discussed with the sponsor.

A female or male patient of childbearing potential cannot be included in the study if there is doubt about strict compliance with contraceptive requirements.

